- If the signed consent is provided as an electronic copy (dropped off at their place of residence) emailed ,photo/scanned to text, or faxed), the participant or LAR must return the original signed document on their first in person visit or by mail if there is no in person visit.
- If the signed consent form is mailed to the consent designee by the participant or LAR, The IRB-approved consent designee will sign their copy which they possess after the participant has acknowledged signature on their copy. Once the participants original copy is received the consent designee copies will be attached to make a single document.
- If the participant signed consent form is provided immediately by electronic format (emailed, faxed or photo/scanned to text, once received, the IRB-approved consent designee signs, dates/times this informed consent document.

We will provide participants with password protected ZOOM links for all meetings.

We will distribute flyers to the Maryland AARP, senior housing residents, African American hair salons, and on Facebook local group and organization sites. A study team member will obtain necessary permission from administrative staff at all locations before any flyers are distributed via postal mail or email.

We will randomize participants to each group with the following process. 1) Once we find potentially interested participants through the above referral sources, we will telephone screen for eligibility and explain study procedures. 2) If eligible by phone, the research assistant will re-screen, re-explain the study, obtain consent (via DocuSign or hard copy ), and conduct the baseline data collection. 4) If participants qualify for the study after this visit, within 48 hours of the baseline interview, we will randomize using a computer-based assignment scheme and communicate the assignment to participants by letter. An employee of the Johns Hopkins Center of Innovative Care in Aging will be unblinded and will complete the randomization for the project. 5) The person assigned to randomize will inform the nurses of the participants' group (intervention or control). 7) The nurses will contact the participant within one week to schedule the first appointment.

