The wait list control group will have data collectors schedule a Zoom video visit with them. The same data will be collected for the intervention group. Participants in the wait list control group will not start the DAPPER intervention until the intervention group has completed the study. The wait list control group will receive monthly phone calls to confirm contact information.

**Data Collectors:** The data collectors have been trained to obtain baseline and outcome measures of each participant. The data collectors will collect baseline and outcome data and are responsible for teaching the participants how to collect saliva samples. The data collectors will call participants to schedule the first Zoom video call. The data collector will call/log on at the mutually agreed time. The data collector will complete the questionnaire booklet with the participant and complete the frailty phenotype measurements

with the participant. If the participants meets the criteria for frailty, pain, and depression, enrollment in the study will continue. Upon completion of the nurses' visits, the data collectors will schedule a final visit with participants.

**Research Nurses:** An RN is the appropriate professional to conduct the visits because of the training in assessment skills, and knowledge base in physiology, medications, and patient education in pain and depressive symptoms. The nurses have been trained on the protocol. The nurses will call the participants to schedule the first visit. The nurses will meet with participants via Zoom video calls during a mutually agreed upon time. The nurses will work with participants to set goals surrounding pain and depressive symptoms. The goals will be participant driven and documented by the nurse. The nurse will then work with the participant to identify strategies to work on three goals.

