**Fidelity Plan:** The fidelity plan is based on the NIH Behavior Change consortium developed by national leaders. All of the nurses and data collectors have received training for the Beat the Blues/Get Busy Get Better Dapper Adaptation Protocol. They have all received training on how to measure frailty using the frailty phenotype. We will enhance fidelity through design elements (intervention is distinct and based on theory), training (using an intervention manual and having formal training), delivery (reminder calls the night before intervention sessions, measure fidelity through records of home sessions (by date and duration), checklists completed by study team members, direct observations concerning intervention engagement to evaluate receipt, and enactment (e.g. participants will show the exercises to the nurses). Ten percent of sessions will be audio taped which will be reviewed by the principal investigator using monitoring checklists developed for this pilot trial. The recordings will not be transcribed. When video visits are done the recordings will be recorded via digital recorder and not via the ZOOM recording feature. Feedback will be provided to each interventionist who will provide case presentations in supervisory sessions. Bi-weekly meetings with the data collectors, registered nurses, and the PI.

**Data collection and management:** We will use the Redcap data entry and management system, which is available to all Clinical Translation Science Award (CTSA) sites such as Johns Hopkins University. Data from screening, intervention sessions, and final data collection will be entered onto forms that the data manager will check for completeness and appropriateness. The data manager will send reports of missing or inappropriate entries to the PI every week for clarification and resolution. The details of the Data Safety and Monitoring plan are in the human subjects section.

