**e.4 Content of Data and Safety Monitoring Reports:** Reports include, at a minimum, study status; descriptions of all SAEs, AEs, UPs, and protocol deviations (including enrollment of an ineligible participant); and any abnormal laboratory, imaging, and other test results. The study PI will attest his/her knowledge to the list of SAEs, AEs, UPs, and protocol deviations completed or that no SAEs, AEs, UPs, and protocol deviations occurred.

The members of the DSMB will be available to offer advice and provide ad hoc consultation throughout the study period. There will be continuous investigator monitoring with prompt incident reporting to the OAIC, Johns Hopkins Internal Review Board, Robert Wood Johnson Foundation, and National Institute of Health (NIH). Evaluation of this trial will include periodic assessments of data quality, participant recruitment, accrual, and retention. All adverse events will be reported to the IRB and the chair of the DSMB within 48 hours if attributable to the study. Members of the DSMB may request an interim analysis of data, which will be presented by the trial biostatistician in a session closed to the PI. The minutes meetings of the DSMB will be reported to Robert Wood Johnson Foundation, NIH, and IRB.

**Adverse Event (AE) Reporting:** The DSMB will be notified by the principal investigator of any serious AE within 48 hours of initial notification to the project team. All members of the DSMB will receive copies of all safety reports at the time of submission to the IRB. In addition, a listing of AEs and their attribution (e.g., level of probability of being study related, intervention related, or unrelated to study or treatment) will be provided to the DSMB on a monthly basis. We do not anticipate any adverse reactions to the intervention. Based on our previous work and studies in this area by others, there is only a small risk that participants will become increasingly anxious to the point that it becomes an adverse event (e.g., harmful to self or others) as a consequence of the activity intervention or having a member of the research team in their home. However, interviewers/interventionists are well trained to manage this reaction or make an effective referral if necessary.

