Given that interviews for data collection and interventions via video, there is the potential for a member of our research team to encounter a potential emergency that is not related to study participation (e.g., dehydration, environmental risk, medical emergency). Following the emergence of the need to account for

such events in behavioral interventions differently than in medical/clinical studies, we refer to such events as “alerts” and have well-developed procedures for their management. All alerts will be reported to the DSMB on a biannual basis. However, the reporting of alerts to the IRB of JHU is not required (see Chart below of potential alert events and plan for their management and reporting).

**Recruitment, AE, and Alert Reports:** Reports presented to the DSMB will include data on enrollment (study accrual by month; comparison of expected to actual enrollment; number of individuals screened, number eligible and number ineligible, number randomized by gender, AEs, and alerts. In addition, the DSMB will receive reports of the number of study participants who discontinue from the treatment group and/or the study and reasons for discontinuation. We propose that reports are provided to the DSMB twice yearly. However, the DSMB will decide upon the schedule of reports. In addition, the DSMB may request reports as needed as well as the unblinding of the data should they deem this necessary. If unblinded efficacy data is required, the biostatistician for this study ([name]) will serve as a liaison between the PI, database, and the DSMB in order to assure that the PI and investigative team remains blinded.

Plan for reporting unanticipated problems or study deviations:

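### The data collectors who measure the outcomes have avoidable routes to learning allocation, and the plan sets no safeguard

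*Combined protocol and SAP*

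**What the plan says.** **Who knows allocation.** The randomization steps under Inclusion/Exclusion Criteria say "An employee of the Johns Hopkins Center of Innovative Care in Aging will be unblinded and will complete the randomization for the project". That person also passes allocation on: "The person assigned to randomize will inform the nurses of the participants' group (intervention or control"). Participants learn their assignment by letter.

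**Who measures outcomes.** The Data Collectors paragraph says "The data collectors will collect baseline and outcome data", and also "The data collector will complete the questionnaire booklet with the participant and complete the frailty phenotype measurements". The same paragraph has the collectors arrange the final visit once the nurse visits are done. The paragraph just before it has collectors arrange a video visit with the wait-list group.

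**Who meets whom.** The Fidelity Plan has nurses present cases in supervisory sessions. It has a tenth of sessions audio-taped, "which will be reviewed by the principal investigator using monitoring checklists". It then ends with "Bi-weekly meetings with the data collectors, registered nurses, and the PI". No agenda or restriction is given.

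**What is said about blinding.** In Section 6, the paragraph on recruitment, AE and alert reports has the biostatistician act as liaison if the DSMB needs unblinded efficacy data, "in order to assure that the PI and investigative team remains blinded". Item e.4 allows a DSMB-requested interim analysis, "which will be presented by the trial biostatistician in a session closed to the PI". Biomarker Procedures states that the assay laboratory is blinded. Nothing comparable is stated for the data collectors.

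**The concern.** The people who record the outcomes should not learn a woman's arm if that can be avoided at little cost. Here they can learn it through ordinary study operations.

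This matters because of how the pilot will be read. Section 5 expects no significant result and bases interpretation on the effect size of the time-by-group interaction, which is meant to inform a definitive trial. If a collector's expectations influence how questions are asked, probed or recorded, or how a walk or grip test is encouraged, the shift enters that effect size directly. A larger sample would not dilute it. The Abstract names pain, depressive symptoms and frailty as the primary outcomes, and these staff collect all three.

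**Working it through.** No formula applies, and the plan gives no figure on this point to reproduce. The check sets the relevant sections side by side.

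1. **Does contact with a nurse reveal the arm?** Yes, in the first period. The wait-list paragraph says controls do not begin DAPPER until the intervention group has finished. Until then, every nurse session, recording or case belongs to an intervention participant.

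2. **Do the nurses know the arm?** Yes. They are told it directly in the randomization steps.

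3. **Do the collectors meet the nurses?** Probably. The Fidelity Plan entry is a fragment without a verb, but a single meeting of the three roles is its natural reading. The frequency term could mean twice a week or every two weeks, and either leaves the point unchanged. Case presentations are placed in supervisory sessions whose attendance is not stated, so the text does not say that cases are presented in the shared meeting. It also does not keep them out of it.

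4. **Does scheduling reveal the arm?** Yes, whatever happens in the meetings. For the intervention group, the collector's cue for the final visit is the end of nurse visits. At 12 weeks a control has had no nurse visits, so her assessment must be cued in another way. The cue itself therefore differs by arm. The separate mention of collectors scheduling visits with the wait-list group points the same way.

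5. **Is there a safeguard?** None is written. The collectors are not said to be masked, the meeting has no restriction, and participants are not asked to keep their group to themselves. The collectors also received the adapted intervention training (Fidelity Plan), so they could recognize its content if a woman mentioned it.

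6. **Could the PI be masked to allocation?** Not under this plan. The PI reviews taped sessions, may be telephoned by treated women about their strategies (Nurse Visit One), and receives weekly data queries that cover intervention sessions (Data collection and management).

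7. **Which outcomes are exposed?** The interviewer-administered questionnaires are exposed at any visit. Gait speed and grip strength are exposed mainly at in-person visits, because the Frailty paragraph assigns the self-report Frail Scale to virtual ones. The documents do not give the share of in-person visits.

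8. **How large is the effect?** The documents give no outcome SD, assumed effect or unblinding rate. Any percentage would be one assumption divided by another, so none is offered.

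**The case against.** The strongest reply is that the plan never promised masked assessors. The sentence about the PI and team staying blinded is conditional on a DSMB request for unblinded efficacy data, and it sits close to the rule that closes interim presentations to the PI. Read together, they most naturally concern comparative results. Hearing a session recording does not reveal those. The plan also gives allocation openly to nurses and participants, so the sentence can hardly mean allocation for the whole team.

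That reply stands, and it limits the point. A reader might infer that the fidelity plan breaks a declared blind. The documents do not support this for the data collectors, because no section declares them blinded. For the PI and nurses the conflict arises only if the sentence means allocation, and the plan does not say which meaning it intends.

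It can also be said that women know their arm and that most outcomes are their own reports, so their own expectations remain whatever the collector knows. This is true, and masking collectors would remove only part of the bias. It does not justify leaving open the part that can be closed cheaply.

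Finally, the shared case discussion is inferred. That is also fair, but the scheduling routes are stated in the text and do not depend on it.

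**Conclusion.** The point holds as a cheap improvement. As written, the plan gives outcome assessors avoidable routes to allocation during the randomized comparison and no safeguard against them. The visit-scheduling route rests on explicit text. The meeting route rests on the natural reading that collectors, nurses and the PI attend together, with nothing to keep cases off the agenda.

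For the collectors the defect is a missing safeguard. For the PI and investigative team it is an ambiguity: if the blinding sentence refers to allocation, it cannot hold for the nurses or for the PI; if it refers to comparative results, it can stand but should say so.

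The size of the bias cannot be estimated from the documents. It matters most for interviewer-administered scores and for gait and grip at in-person visits. It does not invalidate the pilot.

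**What to change.** - **Meetings.** Keep case discussion to meetings of the nurses and the PI. Hold a separate data-quality meeting for the data collectors.
- **Visit triggers.** Have the project coordinator, a role already mentioned in Section 6, trigger assessments in both arms by the 12- and 24-week calendar set in the Abstract and the design overview. Align the Data Collectors paragraph so that completion of nurse visits is no longer the cue, and remove the separate scheduling description for controls.
- **Script.** Ask each participant, at the start of every assessment, not to mention her group.
- **Blinding statement.** State that the data collectors (as far as feasible) and the laboratory are masked to allocation, and that the nurses, the PI and the participants are not. Limit the Section 6 sentence to blinding to comparative results. Claim analyst blinding only if it is actually arranged, since Section 6 has the trial biostatistician present interim data and handle unblinded efficacy data.

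The cost is slightly more scheduling time for the coordinator and one extra short meeting. No added staff, participants or measures are needed.

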#### **4. Drugs/ Substances/ Devices**

N/A

#### **5. Study Statistics**

##### **Sample size calculation and analysis of aims**

**Sample size:** To calculate effect sizes for planning a definitive trial our sample size calculations were based on the need to pilot DAPPER for pain and depressive symptoms. We assume an attrition rate of 13% during the 16-week follow-up based on the CAPABLE trial. Based on these assumptions, an initial sample size of 64 participants (32 in the intervention group and 32 in wait list control) would yield 52 participants (25 intervention, 25 wait list control) after attrition. It is unlikely we will detect a significant difference between the groups due to small sample size and limited follow-up.

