### **1. Abstract**

Older African American women experience disproportionate rates of chronic conditions in comparison to other groups. Pain, depressive symptoms, and frailty often co-occur in African American women aging with chronic conditions and this combination can lead to disability and poor quality of life. Addressing pain and depressive symptoms may improve or delay the progression to frailty. To our knowledge there is little work being done in this population to address both pain and depression. The Depression and Pain Perseverance through Empowered Recovery (DAPPER) program is person directed and will consist of 8 nurse visits during which the nurse assesses each participant for pain, depression, and frailty, then implements a manualized individually tailored intervention. The data collection visits, and nurse visits will take virtually. We propose a pilot trial that is a wait list randomized control pilot to test the acceptability and obtain a preliminary effect size for the intervention. We will recruit 64 ( $\geq$ age 50) African American women who report pain intensity of 3 or higher that interferes with their activities, depressive symptoms lasting more than two weeks, are pre frail or frail, and live in the community/are not institutionalized. The sample will be recruited through the PI's previous study, community recruitment flyers distributed virtually, and word of mouth campaigns. Participants will be randomized into either the intervention or the wait list control group. Once the intervention group has completed their visits, the wait list control group will begin their visits. All participants will be offered the same information and format of nurse visits. The nurses will systematically tailor the content of the visits to the participants' risk profile and goals based on protocols. All participants will be assessed at the start of the study, at 12 weeks, and 24 weeks. The primary outcomes will be pain, depressive symptoms, and frailty status. Other endpoints include goal attainment, stress (cytokines), self-report, self-efficacy, and communication with health care providers. We will also examine the acceptability of the intervention using intervention compliance and one-on-one qualitative interviews. This study will offer either virtual or in person visits based on the preference of the participants.

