### Approach

**4.a Theoretical Framework:** Self-regulation theory is the theoretical framework for this study. Self-regulation theory involves two tenets: 1) participants manage their response based on their experiences (experiences with pain, depression, and frailty treatments) and knowledge of an event and 2) participants' goals are to maintain comfort and decrease the negative effects of an illness (pain depression and/or frailty) on their lives. The intervention is participant centered and participant driven. This means that the participants' experiences and existing knowledge about pain, depressive symptoms, and frailty will drive the goals that they set. For example, a participant may have experienced pain, depression symptoms, and frailty; she is no longer able to go work in her garden. Her goal may be to be able to garden again. This would provide comfort, decrease the effects of these three conditions, and potentially improve her symptoms.

**Design overview of the study:** The design of the study is outlined in the above figure. The outcomes will determine effect sizes on the intervention's effect on pain and depressive symptoms. Outcomes will be measured at 12 weeks (compare intervention and wait list control group) and at 24 weeks (look at outcomes for wait list control group and outcomes over time for intervention group). Goal attainment will be measured at 12 weeks and 24 weeks. At 24 weeks, we will also conduct virtual semi-structured one on one individual interviews with participants to determine feasibility and acceptability.

The intervention group (n=30) will start the study and will receive eight nurse visits that will be focused on decreasing pain, depressive symptoms, and meeting participant selected goals set in these areas. The wait list control group will receive monthly calls by a study team member to ensure their contact information

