##### **Analytic approach:**

For DAPPER, the outcomes will be improvement in pain, depressive symptoms, and communication with health care providers. A database will be created and stored on a password protected encrypted computer. Prior to conducting the analysis, the distribution of the data will be examined to determine if they meet the assumptions of the analytical model and to explore the pattern of missing data. The number of sessions attended will be computed as an indicator of acceptability. To test the effect of the intervention on outcomes (depressive symptoms, pain), generalized estimating equations will be used (GEE) with time, group, and the time x group interaction. We will not be sufficiently powered to detect a significant effect; interpretation of the results will be based on the effect size associated with the time by group interaction for each outcome. One advantage of GEE is it allows all participants' data to be included in the analysis, even those who do not complete the study, providing an intention-to-treat analysis. We will also conduct sensitivity analyses with completers only and compare the effect size to the ITT analysis to estimate the effect size when all participants adhere to the intervention.

Acceptability of the intervention will be examined in multiple ways. We will examine percentages of people who stayed in each arm of the study and conduct numerous descriptive correlational analyses of the

association between the intervention compliance and other variables. These analyses will quantify intervention implementation by demographic and participant health variables. Analyses that utilize the post-randomization data (e.g. treatment compliance) will be evaluated in supplementary analyses. We will distinguish non-compliance with intervention from attrition or loss to follow-up, i.e. missing data. We will also use the one-on-one qualitative interviews to examine acceptability of the intervention.

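### The retained sample does not follow from its own inputs: 64 at 13% attrition leaves about 56, not 52; the printed arms sum to 50; and an intervention arm of 30 conflicts with 32

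*Combined protocol and SAP*

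**What the plan says.** The relevant statements stand in four places.

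- **Study Statistics, sample size paragraph.** The attrition assumption is "We assume an attrition rate of 13% during the 16-week follow-up based on the CAPABLE trial". The next sentence builds on it: "Based on these assumptions, an initial sample size of 64 participants (32 in the intervention group and 32 in wait list control"), and this "would yield 52 participants (25 intervention, 25 wait list control) after attrition". The paragraph then says: "It is unlikely we will detect a significant difference between the groups due to small sample size and limited follow-up".
- **Abstract.** The recruitment target agrees with that start: "We will recruit 64". The schedule is also given there: "All participants will be assessed at the start of the study, at 12 weeks, and 24 weeks".
- **Approach, design overview.** A different arm size appears: "The intervention group (n=30) will start the study and will receive eight nurse visits". No wait-list arm size is given in that section.
- **Study Statistics, analytic approach.** The lack of power is repeated: "We will not be sufficiently powered to detect a significant effect". Results are to be read from the effect size for the time-by-group term. A completers-only sensitivity analysis is planned, and the share retained in each arm is to be reported as evidence of acceptability.

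**The concern.** The sample size paragraph presents its retained number as a consequence of two stated inputs, 64 participants and 13% attrition, yet the result matches neither those inputs nor its own breakdown by arm. The intervention arm also has two sizes, 30 and 32. The attrition period of 16 weeks matches neither planned follow-up assessment, so it is unclear when the retained number is meant to apply.

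No power claim is at stake. What is at stake is a clear planning reference:

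- The safety board reports are to compare planned with actual enrolment, which needs one planned number.
- Retention by arm is reported as acceptability evidence. The paragraph can be read as expecting 87% (the stated rate), 81% (52 of 64) or 78% (50 of 64).
- The retained number is the expected size of the completers-only analysis.
- The pilot is meant to inform a definitive trial, whose planning will need an attrition assumption that can be traced.

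**Working it through.** **Inputs**

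- Starting number N = 64, 32 per arm (Study Statistics; the total is also in the Abstract)
- Attrition d = 0.13 over 16 weeks (Study Statistics)
- Printed result: 52 in total, 25 per arm (Study Statistics)
- Intervention arm of 30 (Approach, design overview)
- Follow-up assessments at 12 and 24 weeks (Abstract)

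**1. Try to reproduce the plan's figure.** Retained = N × (1 − d).

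- Total: 64 × 0.87 = 55.68, about 56. Printed: 52.
- Per arm: 32 × 0.87 = 27.84, about 28. Printed: 25.

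The figure is not reproduced.

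**2. Add the printed arms.** 25 + 25 = 50, not 52. No attrition rate or rounding rule can repair this.

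**3. Attrition implied by the printed results, starting from 64.**

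- 52 retained: 1 − 52/64 = 18.8%
- 50 retained: 1 − 50/64 = 21.9%

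**4. Other routes to the printed figures.**

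| Route | Total | Per arm | Gives 52? | Gives 25 per arm? |
|---|---|---|---|---|
| 64 × 0.87, rounded down within each arm | 54 | 27 | No | No |
| 64 / 1.13 | 56.6 | 28.3 | No | No |
| 64, with 13% at 16 weeks carried to 24 weeks at constant hazard: 64 × 0.87^(24/16) | 51.9 | 25.97 | Yes, if rounded | Only if truncated |
| Start of 60 (30 per arm): 60 × 0.87 | 52.2 | 26.1 | Yes | No |

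The constant-hazard route implies 18.9% attrition by 24 weeks. The plan does not state that step.

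Working backwards at 13%:

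- 52 retained needs 52/0.87 = 59.8, so 60 randomised.
- 25 per arm needs 25/0.87 = 28.7 per arm, or 57.5 in total, so 58 randomised with whole, equal arms.
- Neither is 64.

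From a start of 60, keeping 50 would mean 1 − 50/60 = 16.7% attrition.

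**5. What the gap does to precision.** With equal standard deviations, the standard error of a difference between two arm means is proportional to √(2/n), with n per arm. Going from 28 to 25 per arm multiplies it by √(28/25) = 1.06, about 6% wider. This applies to the completers-only analysis; the main GEE analysis also uses data from people who leave.

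**The case against.** The strongest reply has four parts.

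- **The start is not really in doubt.** The total of 64 appears twice, and the only full split is 32 + 32. No visible text gives a total of 60. The 30 is one arm count in a design overview, so the natural reading is that this line is wrong. This largely stands, and it is why the fix begins by confirming 64.
- **The 52 may have a legitimate origin.** Carrying 13% from 16 to 24 weeks at constant hazard gives 51.9 from 64, and 25.97 per arm, which truncates to 25. This fits 52 about as well as a start of 60 does, and it keeps the stated 64. But the plan ties the 13% to 16 weeks and derives its result from the assumptions as stated. Truncating each arm to 25 still leaves a sum of 50. The route may explain the text but does not make it correct.
- **Little depends on the number.** Power is disclaimed twice, GEE keeps non-completers' data, and no retention threshold is set. This stands and limits the importance of the point.
- **The 16 weeks may describe the trial from which the rate was borrowed.** That is possible. The timing point is therefore a request for clarification and adds no weight to the arithmetic error.

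The design figure is not shown, and some text before the Approach section was not available, so arm sizes given there could not be checked. Neither could make 25 + 25 equal 52.

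**Conclusion.** The concern holds. Three contradictions can be shown from the text alone:

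- 13% attrition from 64 leaves about 56 (28 per arm), not 52.
- The printed arms sum to 50, not 52.
- The intervention arm is 30 in one place and 32 in another.

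The retained number is off by 4 people against the printed total, or 6 against the printed arms. The direction depends on what was meant: if 13% of 64 was intended, expected retention is understated; if 25 per arm was intended, the attrition rate is the wrong figure.

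That the 52 and the arm of 30 are both left over from a plan for 60 participants is an inference. It explains those two figures but not the 25 per arm, and the documents do not mention such a plan. The arithmetic itself needs no assumption beyond applying the stated rate to the stated start. The error should be corrected, but it does not affect the design or the planned analysis.

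**What to change.** 1. Confirm one starting number. The Abstract and Study Statistics support 64 (32 per arm); if that is right, change the arm size in the design overview to 32.
2. In the sample size paragraph, state the attrition rate and whether it applies at 12 or 24 weeks. If a 16-week rate is carried to another time point, show the step.
3. Restate the retained total so that it follows from the rate and equals the sum of its arms:
   - 64 at 13%: about 56 (28 + 28).
   - 25 per arm intended from 64: 50 in total, with attrition stated as about 22%.
   - 60 confirmed as the start, at 13%: about 52 (26 + 26), with the Abstract and Study Statistics changed to 60.
4. Check that any arm sizes in the design figure agree.

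The cost is a text correction in the design overview and the sample size paragraph. If 60 is confirmed instead, the stated recruitment target changes as well. The planned analysis stays as it is in every case.
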